6 SAMPLE SIZE DETERMINATION

We anticipate consenting up to 200 participants to reach 159 randomized participants.

A total sample size of 159 patients (106 pomalidomide, 53 placebo) will provide 94% power to identify a treatment group difference in ESS change from baseline at 24 weeks of 1.0 with $p<0.044$ (per interim analysis alpha spending rules), assuming a standard deviation of 1.7 and 10% early discontinuation rate with the planned MMRM analysis. Power will remain above 80% if there is a substantially higher than expected study discontinuation rate of 30% (with 10% providing no post-baseline data): 81% based on a conservative T-test, or 90% with the planned MMRM analysis. If the standard deviation is 1.8 instead of 1.7, the power for the planned MMRM analysis would be 91% with 10% discontinuation, and 87% with 30% discontinuation.

With 159 patients, we will also have at least 90% power to identify a treatment group difference of 30% for a binary secondary endpoint of proportion of participants requiring at least one packed red blood cell transfusion or iron infusion at any time during the 24-week treatment period with $p < 0.05$, whether assuming a rate in the placebo and pomalidomide groups of 90% vs. 60%, or 50% vs. 20%.

7 STATISTICAL/ANALYTICAL ISSUES

7.1 General Rules

All statistical computations will be performed, and data summaries created using SAS 9.4 or higher. For summaries of study data, categorical measures will be summarized in tables listing the frequency and the percentage of subjects in each study arm; continuous data will be summarized by presenting mean, standard deviation, median and range; and ordinal data will be summarized by presenting median and range.

Estimates from linear models will be presented by mean, standard error, and 95% CI. Estimates from logistic regression will be presented by odds ratios and 95% CIs. All statistical tests will be 2-tailed.

Checks of assumptions (e.g., normality) underlying statistical procedures will be performed and corrective procedures such as use of a transformation or application of nonparametric tests will be applied.

7.2 Adjustments for Covariates

Indicator variables for the study stratification of pooled clinical site (Section 7.6) will be included as a covariate in most efficacy analyses performed for this study (details in Section 9). Also, for all scores analyzed as a change from baseline, the baseline value will also be a model covariate.

Additionally, demographic and baseline characteristics for subjects will be compared between study arms using analysis of covariance techniques for continuous measures, Mantel-Haenszel mean score test using standardized mid-rank scores for ordinal measures, and chi-squared tests for general association for categorical measures. If sample sizes allow, these analyses will control for the study stratification factor of pooled site. If these analyses identify any substantial differences among arms, the use as covariates of these parameters on which the arms differ will be explored in sensitivity analyses of the primary efficacy outcome (see Section 9.3.1).

7.3 Handling of Dropouts and Missing Data

Missing data and missed visits will be monitored in real-time. In the event a scheduled visit is missed, site coordinators will contact the patient before the follow-up window closes to encourage them to at least obtain measurements relevant to the primary endpoint. For any missing data that do occur, we will record and describe the reasons the data are missing when reporting results.

In the event that one or more ESS or QOL visit assessments is missing during the treatment or post-treatment periods, the MMRM analysis approach which assumes data are missing at random (MAR) will be used to compare treatments based on the available data and the correlation between observations within a person. To guard against bias if the MAR assumption is incorrect, missing data mechanisms will be explored, and sensitivity analyses will be conducted on the primary outcome to assess the robustness of the primary analysis (see Section 9.3.1). Sensitivity analyses are not planned for secondary analyses.

7.4 Interim Analyses and Data Monitoring

Safety outcomes will be assessed at each DSMB meeting. Rates of safety outcomes will be compared between treatment groups using Fisher's exact tests and provided to the DSMB. At each meeting, the DSMB will be presented with information about enrollment and outcome data attainment (for

example, the percent of expected visits that have been completed) to allow them to determine that the study is making reasonable progress. These review meeting will occur once each 6 months.

A formal interim analysis for efficacy after 50% and 75% of patients have completed the 24-week treatment period or discontinued from the study. See Section 9.6 for details.

7.4.1 Study Halting Rules

Randomization of new participants will be halted when eight thromboembolic events, defined as any venous thromboembolic event requiring medical intervention (grade 2 or higher) or any arterial thromboembolic event, that are determined to be related or “probably related” to the study drug are reported to the DCC.

The DCC will notify the study monitor, study sponsor, PI and investigators immediately when the eighth thromboembolic event (as defined above) is reported, and randomization functionality will be deactivated. The PI will inform the DSMB members within 24 hours of this occurrence and the DCC will provide the DSMB with AE listing reports. The DSMB will convene an ad-hoc meeting by teleconference or in writing as soon as possible. The DSMB will provide recommendations for proceeding with the study to the study sponsor/NIH. The clinical coordinating center will inform NHLBI and the FDA of the temporary enrollment halt and the disposition of the study.

7.5 Masked Data Review

A masked data review of the primary outcome and secondary outcomes for this study will be performed by the protocol team. This review will occur prior to completion of the primary analyses prior to any official unblinding. This will include a presentation of descriptive statistics (e.g., means, standard deviations, percentiles for continuous variables and counts and percentages of categorical variables) of the selected outcomes and model predictor variables.

7.6 Multicenter Studies

For this multicenter study, randomization of study participants was stratified within center. Consequently, for all model-based primary and secondary analyses, center will be included as a fixed effect in the models, with small centers pooled.

Sites will be pooled based on total number of randomized patients and geographical location prior to unblinding, such that sites with fewer than 10 participants will be pooled, and no pooled site is larger than the largest un-pooled site. If there are several sites with very low enrollment, one pooled site may consist of these sites rather than pooling based on geographical location.

Masked data review prior to database lock identified the following site pooling:

- 1 pooled group of small sites (n=24): Cleveland Clinic (n=7), Johns Hopkins (n=7), UCSF (n=2), Utah (n=6), Florida (n=1) and UCSD (n=1)
- 5 non-pooled sites: MGH (n=51), UNC (n=21), Penn (n=16), Wisconsin (n=12), Mayo (n=21)

As an ancillary analysis associated with the primary outcome, we will examine descriptively whether the treatment effect varies across sites; however, no other analyses will assess site differences in treatment effect because sample sizes are inadequate to support evaluation of site-level effects.

7.7 Multiple Comparisons and Multiplicity

For inferential tests, the p-value for determination of statistical significance (Type I error) for the single primary efficacy outcome (change in ESS from baseline to week 24) will be evaluated relative to 0.044 to adjust for the interim efficacy analysis (see Section 9.6). However, the 75% interim analysis was conducted at 80% due to timing of DSMB meetings. This changed the significance level for the primary outcome from 0.044 to **0.0425** (see Appendix 3).

Significance of the treatment group comparison for 5 key secondary outcomes will be evaluated as follows: If the primary endpoint is found statistically significant at $p < 0.0425$, then the key secondary endpoints will be evaluated for statistical significance with a Hochberg modification to the Bonferroni adjustment (Hochberg, 1988), in which the p-values of the 5 outcomes will be ordered. The largest p-value will be compared relative to $p < 0.05$, and if met, all 5 endpoints will be considered significant. If not, then the second largest p-value will be assessed relative to $p < 0.05/2 = 0.025$, and if met then it and the other three endpoints will be considered significant, and so on for the third p-value compared at $0.05/3 = 0.017$, the fourth compared to $0.05/4 = 0.012$, and the fifth compared to $0.05/5 = 0.010$. Results from analyses of all other secondary endpoints and subgroup analyses will not be evaluated relative to statistical significance.

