11 REPORTING CONVENTIONS

Unless required otherwise by journal standards, the following rules are standard:

- Moment statistics including mean and standard deviation will be reported at 1 more significant digit than the precision of the data.
- Order statistics including median, min and max will be reported to the same level of precision as the original observations. If any values are calculated out to have more significant digits, then the value should be rounded so that it is the same level of precision as the original data.
- Following SAS rules, the median will be reported as the average of the two middle numbers if the dataset contains even numbers.
- Test statistics including t and z test statistics will be reported to two decimal places.
- P-value will be reported to 3 decimal places if > 0.001 . If it is less than 0.001 then report ' <0.001 '. Report p-values as 0.05 rather than .05.
- No preliminary rounding should be performed, rounding should only occur after analysis. To round, consider digit to right of last significant digit: if < 5 round down, if ≥ 5 round up.

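### One Hochberg cut-off for the key secondary endpoints is misprinted: 0.05/4 is 0.0125, not 0.012

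*SAP*

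**What the plan says.** SAP 7.7 defines the family and the method: "Significance of the treatment group comparison for 5 key secondary outcomes will be evaluated as follows". If the primary endpoint meets its significance level of 0.0425, the five are "evaluated for statistical significance with a Hochberg modification to the Bonferroni adjustment".

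The steps are then spelled out:

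- Largest p-value: "The largest p-value will be compared relative to $p < 0.05$, and if met, all 5 endpoints will be considered significant".
- Second: "the second largest p-value will be assessed relative to $p < 0.05/2 = 0.025".
- Third: 0.05/3, shown as 0.017.
- Fourth: "the fourth compared to $0.05/4 = 0.012".
- Fifth: 0.05/5, shown as 0.010.

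Protocol 10.4.9 prints the same five cut-offs. Only the first two steps carry an explicit less-than sign. SAP 7.1 makes all tests two-sided.

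Three rules in SAP 11 bear on precision: "P-value will be reported to 3 decimal places" (when above 0.001), rounding is done only once the analysis is complete, and a digit of 5 or more rounds up.

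**The concern.** A pre-specified decision rule should give one answer for every possible p-value. Here the fourth step is given twice, as a fraction and as a decimal, and the two are not equal. These five endpoints are the only secondary outcomes that SAP 7.7 allows to be judged for statistical significance, so a discrepancy in their thresholds bears on a confirmatory claim.

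The three-decimal display adds to this. A p-value of 0.0122 would be shown as 0.012 beside a printed cut-off of 0.012, and a reader of the table could not tell which way the comparison went.

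**Working it through.** **Inputs.** From SAP 7.7: family-wise level 0.05, five endpoints, k-th largest p-value against 0.05/k, and the printed decimals. From SAP 11: a 5 rounds up. I take the strict inequality of the first two steps to apply throughout.

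**Step 1: reproduce the printed cut-offs.**

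| k | 0.05/k | Three decimals, 5 rounds up | Printed | Printed minus exact |
|---|---|---|---|---|
| 1 | 0.05 | 0.050 | 0.05 | 0 |
| 2 | 0.025 | 0.025 | 0.025 | 0 |
| 3 | 0.016667 | 0.017 | 0.017 | +0.00033 |
| 4 | 0.0125 | 0.013 | 0.012 | -0.0005 |
| 5 | 0.01 | 0.010 | 0.010 | 0 |

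Four of the five reproduce at the precision printed. Only the fourth does not. Truncation would give 0.012 for k = 4, but it would also give 0.016 for k = 3, so it does not explain both figures. Rounding half to even gives both 0.017 and 0.012, but the SAP's stated rule is to round up.

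**Step 2: where the fourth step would differ.** The fraction and the decimal disagree only if the fourth-largest p-value lies in [0.012, 0.0125) and the three larger ones have failed at 0.05, 0.025 and 0.05/3. Take p = 0.2, 0.1, 0.06, 0.0122, 0.004.

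- By the fraction: 0.2, 0.1 and 0.06 fail; 0.0122 < 0.0125 passes. Two endpoints are significant.
- By the decimal: 0.0122 is not below 0.012, so the smallest is tested; 0.004 < 0.010 passes. One endpoint is significant.

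If the smallest p-value were 0.011 instead of 0.004, it would fail at 0.010 and both rejections would be lost.

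**Step 3: the third step, for completeness.** Used literally, 0.017 is slightly lenient for a third-largest p-value in [0.01667, 0.017). With p = 0.2, 0.1, 0.0168, 0.013, 0.011, the fractions give no rejections (0.0168 > 0.01667, 0.013 > 0.0125, 0.011 > 0.010), while the printed decimals give three.

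**Step 4: how often it would matter.** Five two-sided p-values were simulated 4,000,000 times per scenario, and the printed decimals were applied literally. The common correlation and the common mean z are assumptions; the documents give neither. The precondition on the primary endpoint is not modelled. Fewer rejections can come only from the 0.012, and more only from the 0.017.

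| Correlation | Mean z | Calls differ | Fewer rejections | More rejections |
|---|---|---|---|---|
| 0 | 0 | 0.012% | 0.012% | 0.0003% |
| 0.5 | 0 | 0.042% | 0.035% | 0.007% |
| 0 | 2.0 | 1.17% | 0.84% | 0.33% |
| 0 | 2.5 | 0.88% | 0.50% | 0.38% |
| 0.5 | 2.0 | 0.69% | 0.48% | 0.21% |
| 0.5 | 2.5 | 0.63% | 0.42% | 0.21% |

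Under the global null, the probability of any rejection is 0.04890 with exact cut-offs and 0.04888 with printed ones (correlation 0), and 0.04254 against 0.04250 (correlation 0.5).

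**The case against.** The strongest reply is that this is a display matter. Both documents name and cite Hochberg's procedure and print the exact fraction beside each rounded decimal. A statistician programming the test would use 0.05/k. SAP 11 forbids rounding before the analysis is done, so decisions rest on unrounded p-values and the three-decimal rule concerns only how they are shown. That display rule itself gives way to journal standards. On this reading no result is called differently, and the simulated rates describe a use of the decimals that nobody is likely to make. All of this stands.

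It also disposes of two stronger inferences. A reader might conclude that two of the five thresholds are wrong. They are not: 0.017 is what 0.05/3 rounds to at three decimals, and it exceeds the exact bound only if taken literally. A reader might also conclude that a borderline result will be called one way by the formula and another by the plan. The documents do not support that, because nothing in them says the decimals override the fractions.

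The reply does not rescue the 0.012 itself. It is neither the quotient nor the value given by the SAP's rounding rule (which is written for reported results, but is the only one stated). Nor does either document say outright that the fraction governs. The same SAP section restates the primary level from 0.044 to 0.0425, a change of 0.0015; the gap here, 0.0005, is a third of that.

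**Conclusion.** One printed threshold is wrong: 0.05/4 is 0.0125, and SAP 7.7 and protocol 10.4.9 both give 0.012. It would matter only if the decimal were applied literally and the fourth-largest p-value fell in a window 0.0005 wide with every larger p-value already failing. In that case it costs a rejection, so the error is conservative. Under the assumed moderate effects (mean z 2.0 to 2.5, correlation 0 or 0.5), literal use would lose a rejection in about 0.4% to 0.8% of trials. The multiplicity control is sound: even with both rounded decimals used literally, the global-null error rate moves by no more than 0.00005 in the two cases simulated. This is a minor correction to the text, not a flaw in the testing strategy.

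**What to change.** In SAP 7.7, and in protocol 10.4.9 if it is amended, print 0.0125 for 0.05/4. Print 0.0167 for 0.05/3 as well, to match the four decimals used for the primary and interim levels (0.0425, 0.0046, 0.0230). Add one sentence stating that unrounded p-values are compared with the exact 0.05/k. This costs a line of wording, changes neither design nor data, and should be done before unblinding so that no choice between two cut-offs is left open. A fourth decimal or Hochberg-adjusted p-values in the key secondary table would help readers check the calls, but that is optional presentation.

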7.8 Examination of Subgroups

We will evaluate treatment group comparisons for the primary outcome and key secondary outcomes (each in the primary specified analysis population using the primary model and primary timepoint) in subgroups of participants defined by:

- genetic confirmation of HHT (yes or no), defined as having one or more mutations of three primary genes associated with HHT: endoglin (ENG), ACVRL1 and SMAD4
- gender, and
- race (per NIH guidelines), defined as white versus non-white.

7.9 Assessment Windows

For the primary analysis, decisions about how to treat out-of-window visits will be made prior to unmasking data. We intend for all data to be used but will evaluate if any visits fall substantially within another visit window. For secondary analyses, all available data will be used.

8 STUDY PARTICIPANT CHARACTERIZATION

8.1 Participant Disposition

Participant eligibility status will be summarized, and overall disposition of study participants will be described using a standard CONSORT diagram. The number of participants randomized and those completing or discontinuing from study therapy will be summarized. Reasons for study withdrawal will be listed.

8.2 Protocol Deviations

Protocol deviations will be listed with information such as type of deviation, time of occurrence, and reason. The number of protocol deviations will also be summarized overall and for each protocol deviation category.

8.3 Study Drug Exposure and Compliance

All randomized participants will receive the double-blind study drug either at the baseline visit and at subsequent scheduled study visits. The first dose of study drug will be given in the amount of 4 mg pomalidomide or placebo, depending on randomization assignment. Dose can be modified by the investigator (blinded to active versus placebo) in response to side effects to 3 or 2 mg. All bottles contain 28 pills, for a 4-week supply.

The number and percentage of participants receiving each dose level will be presented by visit and treatment group.

Participants are instructed to return their medication bottles after each visit and remaining pills are counted by study staff. Overall study drug compliance will be calculated as the number of pills dispensed minus the number returned divided by the total number that should have been taken from the first dose up until study drug completion or early drug discontinuation. The number and percentage of participants that are at least 80% compliant will be presented. When a participant does not return a bottle, a note is recorded on the CRF as to why it was not returned. The notes will be used to assign an assumed number taken based on that note (for example, all pills taken, or no pills taken)

8.4 Demographic and Baseline Characteristics

Demographic and baseline clinical characteristics and HHT medical history for the study participants will be summarized by study arm using the general analysis rules describe above. Demographic variables of interest include gender, age (years), race and ethnicity, education, employment and marital status, BMI, and baseline levels of all vital signs and QOL measures. Extensive HHT medical history is recorded on a CRF, plus genetic testing.

9 EFFICACY ANALYSES

9.1 Overview of Efficacy Analysis Methods

- All efficacy analyses will be performed on the mITT population, the primary population.
- All efficacy variables will be summarized by treatment group at baseline and at subsequent study time points at which assessments were administered and collected. Count (N), mean, standard deviation, minimum, and maximum will summarize continuous efficacy variables, whereas number and percent will summarize categorical efficacy variables.
- Unless otherwise noted, all analyses of dichotomous outcomes, measured at respective time points, will be performed using models as specified in Section 9.3. Efficacy models will be adjusted for stratification by clinical site. Baseline value will be an additional covariate for all analyses of change from baseline scores. Consistent with the description of the primary analysis in the protocol, analyses of primary and secondary outcomes will also include an independent variable for study visit. For analysis of measures assessed at multiple time points (for example, C1 and C6), longitudinal modeling will be used and the interaction between time and treatment groups will be included. Unless otherwise noted, all analyses of continuous efficacy variables (e.g., ESS and QOL scales) will be performed using general linear mixed models. Variables with distributions substantially different from normal will be transformed prior to analysis.

Models will be adjusted for pooled clinical site. If there are not enough patients per clinical site, similar sites will be combined (see Section 7.6)

9.2 Efficacy Variables

Primary and secondary efficacy variables as well as exploratory and safety outcomes are described in the table below.

Variable	Type	Definition
Primary Outcome		
Change from baseline in Epistaxis Severity Score at each post-baseline visit through 24 weeks and 4 weeks post-treatment	Continuous	
The Epistaxis Severity Score will be computed at baseline and at each study visit during which assessments are administered and collected using the standard scoring algorithm (see Appendix 1). The outcome will then be computed as the difference in score at each visit and the score at baseline. If data at a time point for the assessment are missing, the outcome variable will be coded as missing. The total score be calculated inside the EDC CRF page.

Key Secondary Outcomes		
Amount of iron administered through 24 weeks and 4 weeks post-treatment	Continuous	
The 4-week average amount of iron transfusion (in mg/4 weeks) through 24 weeks will be calculated. For subjects who discontinue early, this value will be pro-rated to 24 weeks. Participants who receive no infusions during the 24 weeks will have a value of zero,
 
In the screening period, the amount of iron received in the 6 months prior to screening is calculated as the number of infusions received multiplied by the amount infused at the last infusion (because the CRF only collected the amount infused at the most recent infusion prior to screening)

Amount of red blood cell administered through 24 weeks and 4 weeks post-treatment This was changed to: proportion of patients receiving at least 1 blood transfusion in the 24-week period.	Continuous Categorical (yes/no)	
The 4-week average amount of red blood cell transfusion (in units/4-weeks) through 24 weeks will be calculated. For subjects who discontinue early, this vale will be pro-rated to 24 weeks.
 
Note: at masked data review, it was determined the overall number of RBC transfusions was small, and this outcome will instead be modified to the percentage of participants that received any RBC transfusion during the 24-week treatment period (and separately, the 4-week post-treatment period)

Change from baseline in Neuro-QoL™ Satisfaction with Social Roles and Activities Short Form (V1.1) T-score	Continuous	The Neuro-QoL™ Satisfaction with Social Roles and Activities Short Form (V1.1) T-score will be computed at baseline and at each study visit during which assessments are administered and collected. Total score

Variable	Type	Definition
Activities Short Form (V1.1) T-score at 12 and 24 weeks and 4 weeks post-treatment		is calculated as a T score using Neuro-QoL online scoring tools (https://www.assessmentcenter.net/ac_scoringservice), where a score of 50 represents the average of the Neuro-QoL calibration sample, which is a general US population, with a standard deviation of 10. The outcome will then be computed as the difference in score at each post-baseline visit and the score at baseline. Missing items within an assessment are handled by the official online scoring tools.
Change from baseline in HHT QoL Total Score at 12 and 24 weeks and 4 weeks post treatment	Continuous	The HHT QoL Total Score will be computed at baseline and at each study visit during which assessments are administered and collected by summing all of the items (Kasthuri et al 2022). The outcome will then be computed as the difference in score at each post-baseline visit and the score at baseline. If any data items at a time point for the assessment are missing, the outcome variable will be coded as missing.
Change from baseline in average daily epistaxis duration 8-12 and 20-24 weeks and 4-weeks post-treatment	Continuous	The average daily epistaxis duration will be computed at baseline and at each study visit during which the epistaxis diary is collected (See Appendix 2). The outcome will then be computed as the difference in average at each post-baseline visit and the average at baseline. If data at a time point for the assessment are missing, the outcome variable will be coded as missing. The daily average is calculated by averaging all non-missing data across all available days in a diary. At least 7 total days for each diary must be present in order to calculate the average for that time period. If the actual number of minutes for a nosebleed is not provided but the duration category is checked, then the midpoint of the duration category will be used as the duration for that nosebleed as follows: <1: 0.5, 1-5: 3, 6-15: 10.5, 16-30: 23, 31-60: 45, > 60: 60 Note: at masked data review, the unit of this outcome was modified from weekly to daily.
Other Secondary Outcomes		
Change from baseline in PROMIS® Emotional Distress-Depression Short Form (V1.0) T-score at 12 and 24 weeks	Continuous	The PROMIS® Emotional Distress-Depression Short Form (V1.0) T-score will be computed at baseline and at each study visit during which assessments are administered and collected using the PROMIS online scoring algorithm (https://www.assessmentcenter.net/ac_scoringservice).

Variable	Type	Definition
and 4 weeks post-treatment		A score of 50 represents the average of the PROMIS calibration sample, which is a general US population, with a standard deviation of 10. The outcome will then be computed as the difference in score at each post-baseline visit and the score at baseline. Missing items within an assessment are handled by the official online scoring tools.
Change from baseline in PROMIS® Fatigue Short Form (V1.0) T-score at 12 and 24 weeks	Continuous	The PROMIS® Fatigue Short Form (V1.0) T-score will be computed at baseline and at each study visit during which assessments are administered and collected using the PROMIS online scoring algorithm (https://www.assessmentcenter.net/ac_scoringservice). A score of 50 represents the average of the PROMIS calibration sample, which is a general US population, with a standard deviation of 10. The outcome will then be computed as the difference in score at each post-baseline visit and the score at baseline. Missing items within an assessment are handled by the official online scoring tools.
Proportion of patients with RBC transfusions or iron infusions through 24 weeks. The treatment goal is receiving none (a value of No).	Dichotomous (Yes/No)	The number of iron infusions and RBC transfusions will be counted throughout the 24-week treatment administration. The outcome is calculated as “No” if no transfusions/infusions, and “Yes” if ≥ 1 transfusion/infusion.
Proportion of patients requiring endoscopic intervention through 24 weeks	Dichotomous (Yes/No)	
The number of endoscopic interventions for management of bleeding will be counted throughout the 24-week treatment administration. The outcome is calculated as “Yes” if ≥ 1 endoscopic intervention and “No” if no endoscopic interventions.
 
Endoscopic interventions are recorded by the site on the concomitant medications form, can be either nasal or gastroenterological interventions. Identification of endoscopic interventions (such as nasal cauter) will be confirmed by medical review. These were identified prior to database lock and include endoscopy, cauter, and embolization.

Incidence and Severity of Specific adverse events	Discrete	The incidence rate and maximum severity of the following adverse events will be calculated: MedDRA terms identified in blinded data review noted for each.

Variable	Type	Definition
		
 • Venous thromboembolism 
 ◦ Portal vein thrombosis, Deep vein thrombosis • Arterial thromboembolism 
 ◦ None found • Thrombocytopenia 
 ◦ Thrombocytopenia • Neutropenia 
 ◦ Neutropenia ◦ also Leukopenia, and also a category of (Neutropenia or Leukopenia) • Peripheral neuropathy 
 ◦ Neuropathy peripheral, Peripheral sensory neuropathy • Fatigue 
 ◦ Fatigue • Constipation/diarrhea 
 ◦ Constipation, Diarrhoea, Nausea, Abdominal pain • Rash 
 ◦ Rash popular, Rash pruritic, Rash maculopapular, Rash, Rash erythematous, Urticaria, Pruritus, Palmar erythema • Any other AEs or SAEs of at least moderate severity that are possibly related to pomalidomide and deemed medically relevant at masked data review: 
 ◦ Pulmonary embolism ◦ Mouth ulceration ◦ Alanine aminotransferase increased ◦ Tremor ◦ Dyspnoea and exertional dyspnoea (only the cases that meet criteria of at least possibly and at least moderate) ◦ Tachycardia (only the cases that meet criteria of at least possibly and at least moderate) ◦ Muscle spasms (only the cases that meet criteria of at least possibly and at least moderate)
Change from baseline in iron (transferrin) saturation, ferritin, hemoglobin, hematocrit, MCV, and MCHC.	Continuous	Lab parameters are analyzed at each site (including at local labs) and entered onto CRFS in the EDC system. Transferrin Saturation is calculated within medidata from Iron and Iron Binding Capacity.

Variable	Type	Definition
		The outcome will then be computed as the difference in value at each post-baseline visit and the value at baseline.
Thrombocytopenia platelet categories	Categorical Normal < 150 K/uL < 100 K/uL < 50 K/uL	Added as additional planned safety presentation at blinded data review meeting. Categorical assessment of thrombocytopenia will be calculated based on all platelets collected post-baseline. A person will be classified into one of the 4 categories based on the lowest recorded post-baseline platelet value. The value of 150 represents the lower normal bound.
Neutropenia neutrophils categories	Categorical Normal < 1.45 K/uL < 1.00 K/uL < 0.50 K/uL	Added as additional planned safety presentation at blinded data review meeting. Categorical assessment of neutropenia will be calculated based on all neutrophils collected post-baseline. A person will be classified into one of the 4 categories based on the lowest recorded post-baseline neutrophil value. The value of 1.45 represents the lower normal bound.
Exploratory Outcomes		
Relapse at 4-weeks post treatment	Dichotomous (Yes/No)	The rate of relapse will be calculated at 4 weeks post-treatment. Relapse is defined as a return of the ESS to the baseline value or greater.
Treatment weeks to 1.0 decrease in ESS	Ordinal Categorical (4, 8, 12, 16, 20, 24, Not obtained)	The time to the first 1.0-unit decrease in ESS will be calculated for each participant by computing the difference between the baseline ESS and the ESS at each study visit and determining the first study visit at which the difference is ≤ -1.0 , or “not obtained” if no visit had an improvement of at least 1.0
Oral iron taken during the treatment period	Categorical (Always taken, Never taken, Added after baseline, Stopped after baseline)	All oral iron supplements will be identified from the concomitant medications form (using search for Iron, Fe, ferrous, Ferrous Sulfate) and confirmed by medical review. Oral iron usage will be categorized for each participant as always taken if it was taken during the screening period before baseline, and also taken post-baseline, added after baseline if it was started after the date of the baseline visit, stopped after baseline if it was stopped after the baseline visit, and never taken if a patient had no oral iron recorded.
Other outcomes		

Variable	Type	Definition
Other outcomes include individual questions on the ESS and the diary and iron studies not otherwise covered in a secondary or exploratory outcome		
Nosebleed frequency, duration, and intensity (ESS items 1-3) at each visit	Categorical	Reported as recorded on CRF, categories may be combined based on observed data and to assist in trend interpretation.
Sought medical attention for nose bleeding (ESS item 4) during the 24-week treatment period	Dichotomous (Yes/No)	"Yes" if reported at any visit C1-C6 and "No" if not reported at any visit C1-C6
Anemia (yes/no) (ESS item 5) at each visit	Dichotomous (Yes/No)	Reported as recorded on CRF
Iron replete status by visit, defined as a ferritin ≥ 50 ng/ml and a transferrin saturation $\geq 30\%$	Dichotomous (Replete/Not replete)	Iron replete status is defined as replete if ferritin ≥ 50 ng/ml and a transferrin saturation $\geq 30\%$ and is defined as "not replete" if either ferritin < 50 ng/ml or transferrin saturation $< 30\%$.
Hemoglobin below 6.5 gm/dl at any time during the 24-week treatment period	Dichotomous (Yes/No)	A blood transfusion was mandated for a hemoglobin below 6.5 gm/dl.
Diary frequency, duration and intensity questions	To be determined	Presentation of data on frequency, duration and intensity questions collected for each nosebleed on the diary will be considered as a secondary item after analyses specified in the SAP are completed.

